treatment. The target therapeutic dose (8 mg doxazosin) will be achieved after an 18-day dose escalation schedule. Medication will be distributed across 6 visits. Participants will be provided 3-5 days of extra pills of their current dose at each distribution to provide flexibility in missed appointments; however, participants will not receive their next escalated dose until they attend an in-person visit. On study completion all participants will taper off doxazosin (or placebo) over 5 days using a protocol successfully employed by our consultant [name] in a recently completed smoking cessation trial. Participants who withdraw from the study will be tapered using the same protocol. There are no adverse effects with rapid cessation that may occur in other noradrenergic drugs (e.g., propranolol rebound hypertension)¹³¹.

C5. Medical Monitoring And Medication Compliance

[figure not shown]
Participants' safety will be evaluated by the study staff and medical staff via measurement of vital signs and self-report of medication side effects, adverse events, medication compliance and alcohol use at each of the three Study Visits (Day 1, 29, 57). Study staff will call participants on Day 2 to monitor (via self-report) adverse events and initial compliance with taking the first pill on Day 1. In addition, participants will attend four additional Medical Monitoring Visits at the UW Hospital the day of each dose escalation (Day 6, 10, 14, 18) for similar evaluation. As such, participants are evaluated in person prior to each dose escalation and at 4 weeks and 8 weeks into treatment.

Participants will complete safety check-ins weekly between Study Visit 2 and 3 (Day 36, 43, 50) to evaluate safety via self-report of medication side effects, adverse events, medication compliance, and alcohol use. These check-ins can occur via phone call or electronic survey according to participant preference. For participants who opt for electronic surveys, study staff will follow-up via phone if the participant reports side effects or problems or if the participant does not complete the survey. While we anticipate that subjects will tolerate study medication well, should participants experience adverse medication side effects, titration will be stopped at the highest tolerable dose. Maximum achieved dose will be included as a covariate in preliminary statistical models.

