- **5. Side effects from study medication (doxazosin):** The most common side effects associated with doxazosin are drop in blood pressure, dizziness, headache, drowsiness, lack of energy, weakness, palpitations, and nausea. Orthostatic hypotension and syncope (i.e., fainting) can occur in some individuals. Alpha1-NE antagonists have been associated with the so-called "first-dose phenomenon" whereby the possibility of fainting is higher after the first dose in 1% of the population. Syncope risk is increased with dehydration, especially when moving from lying or seated to standing. It is also possible that orthostatic hypotension and syncope could occur after the first dose following increase in dosage, or if therapy with the drug is interrupted.

One rare but serious side effect is priapism, which is a painful penile erection sustained for hours, that can lead to permanent impotence/erectile dysfunction if not promptly treated. The prescribing information for doxazosin suggests that this risk occurs less than once every several thousand people.

- **6. Confidentiality failure**: The questionnaires and psychophysiological measures to be used in the proposed research are generally of a benign nature. However, some self-report questionnaires yield sensitive information regarding alcohol use. If confidentiality is broken the information collecting in this study could have unanticipated or untoward consequences for the participant's reputation, employability, or legal status.
- **7. Alcohol craving following stressor exposure**: Participants are exposed to a stressor task (the NPU Task) during study visits 1 and 2. It is possible that this stressor could elicit mild, brief alcohol craving in study participants.

D2. Adequacy of Protection against Risks:

In this section, we outline the protections in place to reduce the risk associated with the risks identified in D1.

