Study staff will have direct contact with participants on 10 occasions during the 8-week study period to assess for any adverse events, medication side effects, and answer questions about treatment. This includes three Study Visits (Day 1, 29, 57), four Medical Monitoring Visits (Day 6, 10, 14, 18) and four Safety Check-ins via phone or electronic survey (Day 2, 36, 43, 50). All study visits will be conducted in the University of Wisconsin-Madison Hospital CRU under medical supervision. A registered nurse will be present in the CRU during all study visits to monitor for drug side effects and provide appropriate medical attention. Orthostatic vital signs will be checked by CRU-RN at all study visits. Any participants experiencing significant side effects will be withdrawn from the study and provided medical attention from the study nursing staff and/or physician as needed. Adverse events will be monitored, and "stopping rules" will be applied if needed (see Stopping rules).

Participants will be educated about potential side effects of doxazosin and ways to mitigate risk. For instance, to reduce the risk of syncope upon standing from bed in the morning, participants will be instructed to slowly sit up and stay on the edge of their bed for 5 minutes before standing following the initial doses of doxazosin. Additional instructions will encourage participants to keep well-hydrated and urinate while sitting down rather than standing. They will be strongly discouraged from driving or operating heavy machinery within 24 hours of the first dose, or at any dose escalation.

It will be recommended that participants continue to take doxazosin before bed, however clinical research has shown that doxazosin is safe to take in morning or evening and with or without food. Doxazosin is not sedating nor are there concerns of rebound hypertension following rapid cessation of use that occur with other noradrenergic agents, such as clonidine¹³¹.

If symptoms of hypotension (such as dizziness) are reported, the participant will be encouraged to increase fluid intake if a negative fluid balance may be playing a role. If hypotension is noted in the CRU settings, the medical staff, upon the study physician orders, is able to place a peripheral venous access and administer IV fluids, such as normal saline, that can provide an effective treatment for orthostatic hypotension.

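### The protocol names interrupted doxazosin as a syncope setting, but its bedside and driving precautions, as written, do not extend to restarting 8 mg after missed doses

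*Combined protocol and SAP*

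**What the plan says.** The side-effect item in D1 (Potential Risks) describes fainting after the first dose. It then adds that orthostatic hypotension and "syncope could occur after the first dose following increase in dosage, or if therapy with the drug is interrupted". The protocol therefore recognises three settings: first dose, dose increase and interruption.

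D2 (Risks from study medications) gives the matching precautions. Participants are told to "slowly sit up and stay on the edge of their bed for 5 minutes before standing following the initial doses of doxazosin". On driving, the text is "They will be strongly discouraged from driving or operating heavy machinery within 24 hours of the first dose, or at any dose escalation". One sentence carries no dose limit: "Additional instructions will encourage participants to keep well-hydrated and urinate while sitting down rather than standing". Bedtime dosing is also recommended without a limit.

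The dosing and monitoring rules are in C4 and C5. C4 sets one condition on stepping up: "participants will not receive their next escalated dose until they attend an in-person visit". It allows for late visits by supplying spare capsules at the existing strength: "Participants will be provided 3-5 days of extra pills of their current dose at each distribution to provide flexibility in missed appointments". C5 adds that "participants are evaluated in person prior to each dose escalation". Titration is stopped, slowed or capped when side effects occur (C5 and D2). Pill counts and smart-cap logs are read at visits. Daily texts ask participants to get in touch about side effects or obstacles to taking the medication. Weekly check-ins on Days 36, 43 and 50 ask about compliance. For those who choose the electronic version, "study staff will follow-up via phone if the participant reports side effects or problems or if the participant does not complete the survey".

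**The concern.** Of the three settings named in D1, the third has no matching response in D2, C4 or C5. The gap is plainest after Day 18, when the participant has 8 mg supplies at home. Someone who misses several nights and resumes 8 mg is taking neither a first dose nor an escalated one. The two precautions aimed at the moment of greatest risk therefore do not apply as written, and nothing in the protocol body tells the participant to call first or tells staff what to do on learning of the gap.

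What is at stake is safety: falls, or fainting while driving, at the highest dose in the trial. The situation is foreseeable, since A6 itself calls medication compliance a major obstacle in this population.

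**Working it through.** **Step 1: match each protection to its trigger.**

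| Protection | Section | Trigger | Reached by an 8 mg restart at home? |
|---|---|---|---|
| 5-minute bedside step | D2 | initial doses | not as written |
| 24-hour driving warning | D2 | first dose, escalation | no |
| Hydration, seated urination | D2 | none (always) | yes |
| Bedtime dosing | D2 | none (always) | yes |
| Hold on escalation | C4 | visit not attended | no; the dose is not escalating |
| Stop, slow or lower titration | C5, D2 | side effects | only after symptoms |
| Contact staff at once | D2 | adverse event | only after symptoms |
| Daily text and cap reminder | C5 | sent every day | yes, as a reminder; no restart instruction described |
| Pill count, cap log | C5 | study or monitoring visit | read on Day 29, then Day 57; no action stated |
| Check-ins | C5 | Days 36, 43, 50 | compliance is asked about; no action on missed doses stated |

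No row has missed doses as its trigger.

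**Step 2: how long the exposure lasts (Table 2).**
- Days at 8 mg: 56 − 18 + 1 = 39; 39/56 = 69.6% of treatment days.
- Intervals between objective compliance readings in that period: 29 − 18 = 11 days, then 57 − 29 = 28 days. Self-reported compliance is also asked about on Days 36, 43 and 50.
- The 90% compliance bonus (C3) allows a sizeable gap. If it is counted over 56 doses (assumed), 51/56 = 91.1%, so five missed doses still qualify, consecutive or not.

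**Step 3: rough size of the gap.** Input: half-life 16-22 h (A6). Assumption: linear one-compartment kinetics at steady state. The pre-dose level after n missed nights, as a share of usual, is 0.5^(24n/half-life). The equivalent steady daily dose is 8 mg times that share.

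| Missed nights | Share at 16 h | Share at 22 h | Level as on (mg/day) |
|---|---|---|---|
| 1 | 35.4% | 47.0% | 2.83-3.76 |
| 2 | 12.5% | 22.0% | 1.00-1.76 |
| 4 | 1.6% | 4.9% | 0.12-0.39 |

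For comparison, Table 2 starts at 1 mg, its largest step is 2 mg (1, 2, 4, 6, 8), and each step follows an in-person evaluation.

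**Step 4: a less common case, a late Day 18 visit.** The 6 mg supply covers Days 14-17. With 3-5 spares and no leftover capsules used (assumed), it ends on Day 20 to 22. A return by Day 21 (3 spares) or Day 23 (5 spares) misses nothing. A return on Day 25 (assumed) is 7 days late and follows 7 − 3 = 4 or 7 − 5 = 2 missed nights, and Table 2 then makes 8 mg the next dose. The prior level is 6 mg times the shares above: 0.75-1.32 mg/day (2 nights) or 0.09-0.29 mg/day (4 nights). Here the in-person evaluation, the compliance check and the driving warning do apply, but no decision is tied to the gap.

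**The case against.** Five points can fairly be made for the plan.

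- D2 introduces the bedside step as an example of participant education, not as a complete list, and its reference to initial doses in the plural could be stretched to a restart. This stands in part: the education given may be wider than the text. The driving warning is not introduced as an example, however, and resuming the same 8 mg is neither of its two triggers.
- The consent form, information sheet, package insert and a health-facts sheet are handed to participants (Appendix B), and none is reproduced. This stands. A reader might infer that a participant could obey every written instruction and still restart unprotected. The documents do not support that, because most of what participants receive in writing cannot be seen.
- A reader might infer from the 28-day interval that nobody asks about missed doses in that time. That is not so: compliance is asked about weekly, and staff could reasonably treat missed doses as a problem that warrants a call. What is absent is a statement that they should.
- The kinetics show no syncope risk. This also stands. The documents relate no level to fainting, and the only figure given, 1% in D1, concerns the first dose. By the size of Table 2's steps even one missed night would look large, so no particular cut-off follows from the arithmetic.
- The protocol says abrupt cessation is harmless. That concerns stopping and rebound hypertension; the hazard here is restarting.

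**Conclusion.** The gap is real but narrow. The protocol body names a hazard and gives two dose-triggered precautions that leave it out, and it attaches no action to missed doses. The period affected is Days 18-56, at the highest dose. The number of participants affected is unknown, and no rate of syncope on restart can be taken from the documents.

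The conclusion rests on the plain reading of the triggers in D2 and on an inference that a participant with 8 mg capsules at home would resume at 8 mg. The protocol does not instruct this, but Table 2 schedules that dose and no rule says otherwise. The decay figures show scale only.

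A reader might go further and conclude that a mandatory hold and re-titration after a set number of missed doses is required. The documents do not support that: no level-syncope relation is given, and such a rule would bring extra dispensing and visits. This is an inexpensive safety improvement that should be made, not a flaw in the dosing schedule itself.

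**What to change.** In D2:
- Extend the bedside instruction and the 24-hour driving warning to the first dose after an interruption.
- Tell participants to call staff before restarting after consecutive missed doses, with the number set by the study physicians. Two is a reasonable proposal: the pre-dose level then lies at or above the equivalent of Table 2's 1 mg step and below its 2 mg step.

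In C4 and C5:
- List missed doses as a problem that prompts a staff call after an electronic check-in.
- Review the pill count and cap log before dispensing an escalated dose. If there is a gap, the study physician decides, blind to arm, whether to proceed.

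Do not add a fixed hold or re-titration rule. Check that the handouts agree with the revised text.

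The cost is protocol wording, a change in the order of checks already made, and occasional physician calls. At the physician's discretion, some participants may need extra dispensing or visits, or may be below 8 mg at Visit 2; how many is unknown. Participants hold only 4 mg capsules after Day 29, so most lower restart doses would need new blinded supplies.

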Participants will be encouraged to continue whatever treatment for alcohol use they were receiving prior to study enrollment throughout the duration of the study. They will be instructed that the study medication is not approved as pharmacotherapy for their alcohol use disorder and therefore will not substitute for their existing treatments and other supports. Participants will be instructed to contact the study staff immediately if they experience any adverse events during these 8 weeks. The study physician will make medical recommendations as appropriate to handle the adverse events. The UW Pharmaceutical Research Center will break the drug blind to inform the participant and study physician if a situation arises where this information is critical to providing appropriate medical care.

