Monitoring the progress of study and the safety of participants. The Principal Investigator will be responsible for routine monitoring of the study's progress. This includes scheduled monthly meetings with

study staff and the study MD, and review of written documentation. Data that are reviewed at these meetings include the number and type of participants enrolled, the number and reasons for exclusions from enrollment, the number treated and the stage of treatment, summary of adverse events, individual review of serious adverse events and study participation and outcome data. In addition, any unanticipated health events that raise concerns (e.g., serious mood or behavioral changes, suicidal ideation, abnormal test results) will be immediately reported to the PI and the study physicians.

To facilitate participant safety, study participants must meet study eligibility criteria. Once enrolled, study protocol will assess for the presence of adverse events at each study visit by querying participants as to whether they have experienced any adverse side effects associated with study medications. Participants who report development of severe side effects associated with doxazosin (which is unlikely) will be discontinued from further study participation as a precaution. Such events will be immediately reported to the PI and study physicians. If significant psychiatric or medical symptoms are reported, the participant will be referred, as needed, to the appropriate emergency medical or psychiatric services.

Stopping rules. Study will be stopped if two patients experience SAEs diagnosed to be related to the study drug and affect same organ system (e.g., cardiac, hepatic, renal or central nervous system). More specific examples are a three-fold elevation above baseline of serum liver enzyme (hepatic function) and creatinine (kidney function) levels, and QTc interval prolongation over 500 ms (or 50 ms increase over baseline) or other documented serious ECG abnormalities.

The study would resume after thorough evaluation and if it is deemed that the continuation of study activities is determined safe to participants by the study physicians, the study investigators, the IRB, and the funding agency representative.

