Plans for assuring compliance with requirements regarding the reporting of adverse events. This Data Safety and Monitoring Plan requires that investigators notify NIH and the University of Wisconsin IRB of the occurrence of any serious adverse event (SAE), or any adverse event (AE), which is severe, unexpected, and possibly related to study medication or protocol. Such notification must occur within five days of investigators becoming aware of the event. If the serious adverse event might be related to drug use, both the Food and Drug Administration and the manufacturer will also be notified within five days of investigators becoming aware of the event. Examples of serious adverse events would be untoward medical or treatment occurrences that result in death, are life-threatening, require hospitalization or prolonging of existing hospitalization, create persistent or significant disability/incapacity, or involve congenital abnormality/birth defects. Unanticipated adverse events would include less serious problems that merit reporting because they are severe, unexpected, and possibly related to study participation. Any serious adverse event (SAE) will be queried and reported even if it appears that the serious adverse event is unrelated to treatment participation. The PI will be responsible for the accurate documentation, investigation and follow-up of all study-related adverse events.

Adverse event assessment, recording, reporting and investigation will be accomplished through staff training, structured or standardized assessments of untoward occurrences/events, and regular monitoring by study investigators. The Principal Investigator has ultimate responsibility for ensuring that serious adverse events are detected and reported in a timely manner. All serious or unanticipated adverse events will be reviewed by the study physicians. Additionally, the IRB will receive an annual report of all serious adverse events and adverse events meeting the criteria listed above.

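### The only stated way of asking about adverse events at study visits is limited to side effects of the study drug, which is narrower than the rest of the safety plan requires

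*Combined protocol and SAP*

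**What the plan says.** D5, under monitoring of progress and participant safety, gives the method for study visits: adverse events are assessed by "querying participants as to whether they have experienced any adverse side effects associated with study medications".

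Other places describe the scope differently:

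- **C5 (medical monitoring), study visits.** Safety is evaluated by vital signs and "self-report of medication side effects, adverse events, medication compliance and alcohol use at each of the three Study Visits". Side effects and adverse events are two items.
- **C5, monitoring visits.** Participants attend on "the day of each dose escalation (Day 6, 10, 14, 18) for similar evaluation".
- **C5, check-ins on Days 36, 43 and 50.** These are made by phone or electronic survey "to evaluate safety via self-report of medication side effects, adverse events, medication compliance, and alcohol use".
- **D2, risks from study medications.** Staff contacts are "to assess for any adverse events, medication side effects, and answer questions about treatment", and "Participants will be instructed to contact the study staff immediately if they experience any adverse events during these 8 weeks".
- **D5, reporting.** "Any serious adverse event (SAE) will be queried and reported even if it appears that the serious adverse event is unrelated to treatment participation". Assessment is to use "structured or standardized assessments of untoward occurrences/events", with no instrument named.
- **Table 1.** Adverse events are listed at study visits, monitoring visits and staff calls, with no condition on cause.

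Two further places lean the narrow way. The D5 reporting text words the principal investigator's duty to document, investigate and follow up in terms of adverse events related to the study. The daily phone reminders in C5 ask participants to contact staff about side effects or obstacles to taking the medication.

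**The concern.** The D5 wording puts the question of cause before the question of occurrence. Someone asked about side effects of the study medication has no reason to mention a fall after drinking, an injury or an emergency visit put down to something else. Sound practice runs the other way: record what happened, then have a blinded clinician judge whether the drug could be responsible. That order matters most for reactions that nobody yet expects from the drug in this population.

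What is at stake is mainly the completeness of the safety record. There is a secondary issue. Participants are told the common side effects of doxazosin before consent (D2), and the package insert is a listed handout (Appendix B). If reporting depends on believing that an event is due to the drug, a participant's guess about treatment can influence what is recorded. A neutral question largely removes that route.

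**Working it through.** No figure in the plan bears on this, and no arithmetic beyond a count of contacts applies. The check is a comparison of the sections.

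**1. Which contacts the D5 sentence governs.** D2 lists three study visits (Days 1, 29, 57), four monitoring visits (Days 6, 10, 14, 18) and four check-ins (Days 2, 36, 43, 50): 3 + 4 + 4 = 11 contacts, although D2 itself gives the total as 10. The D5 sentence refers to study visits. Read strictly, it covers 3 of the 11, and the other 8 rest on C5, D2 and Table 1.

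**2. Subject matter or method.** C5, D2 and Table 1 say *what* is to be assessed, and list adverse events apart from side effects or without any condition on cause. Only D5 says *how* the participant is asked. The structured assessment promised in D5 could supply a broader question, but it is not identified. Appendix A lists questionnaires and interviews on drinking, craving, mood, withdrawal and diagnosis, and no adverse-event form. A person writing the visit script from this protocol has one sentence to work from.

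**3. Two readings of that sentence.**

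- *The participant decides the link.* An event blamed on anything else is not an answer.
- *Side effects known for the drug.* The participant makes no causal judgement, but an event outside the known profile, such as an injury or an unrelated illness, is still not an answer.

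Both readings are narrower than the scope in C5 and D2.

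**4. Kinds of event against the routes described.**

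| Event | D5 visit question, literal | Other route in the plan |
|---|---|---|
| Dizziness, palpitations and similar (D1 list) | Captured | C5, D2 |
| Hospital stay blamed on drinking | Not elicited | D5 query of all serious events |
| Non-serious fall, emergency visit or illness not linked to the drug | Not elicited | Adverse-event item in C5 and D2, wording not given; spontaneous report |

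The exposed category is the last row: non-serious events that the participant does not attribute to the drug.

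**5. How much independent detection there is.** Table 1 schedules blood chemistry and ECG at Study Visit 1 only. After that, scheduled safety detection is mainly vital signs and self-report. D1 and the data collection section say research material comes directly from participants, without archival records, so no record check is described for an event that goes unmentioned. Between Days 29 and 57 the scheduled contacts are phone or electronic check-ins, where the wording of the question carries most of the weight.

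**6. Size.** The documents contain no expected adverse-event rate, no attribution rate and no planned check of treatment guess. Neither the number of missed events nor any difference between arms can be calculated from them.

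**The case against.** The strongest reply is that D5 is narrative, not a script, and that the plan as a whole is broader. This is largely right. Participants are told to report any adverse event at once. C5 and D2 list adverse events separately. D5 also sends unanticipated health events of concern, such as mood changes or abnormal tests, to the principal investigator and study physicians. Scripts are not among the documents, so the wording used in practice may be adequate. What remains is that the one sentence describing the question disagrees with those sections, and nothing named settles the disagreement.

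A reader might infer more than the documents support:

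- **That adverse events are found only through attributed side effects.** C5, D2 and the D5 reporting text all provide wider routes.
- **That the stopping rule counts only events that passed this question.** The rule counts serious events diagnosed as related to the drug. All serious events are to be queried and are reviewed by the study physicians. The rule's specific examples are laboratory and ECG findings, which no side-effect question would elicit.
- **That the safety comparison between arms is biased by some amount.** Participants and research staff are blinded, the handout list makes no distinction by arm, and the Statistical Analysis section plans no adverse-event comparison by arm. An effect of treatment guesses is possible, but any figure for it would rest on invented inputs.

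**Conclusion.** The conflict is real and should be corrected. D5 states a question narrower than C5, D2, Table 1 and its own reporting text require, no named instrument fills the gap, and the documentation duty is worded for study-related events. Taken literally, D5 could miss mainly non-serious events that participants do not connect with the drug.

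This conclusion assumes that the D5 sentence would guide the visit scripts. If the unnamed structured assessment already asks an open question, the defect is one of documentation only. The shortfall cannot be sized, and the planned analyses of startle potentiation and heavy drinking are not affected.

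**What to change.** Reconcile C5, D2 and D5 around a single procedure:

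1. Replace the D5 question with an attribution-neutral one: any new or worse health problem, injury, emergency visit or hospital stay since the last contact, whatever the cause.
2. Follow it with a fixed list of the expected effects given in D1 under side effects from study medication. Asking the open question first avoids steering the answer.
3. Use the same wording in both arms and at every study visit, monitoring visit, call and electronic check-in, and add the form to Appendix A.
4. Record all adverse events, and reword the principal investigator's documentation duty to match.
5. Have the blinded study physician assign relatedness afterwards.

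The cost is a change of wording in the protocol and scripts and slightly more adverse-event recording. No extra visit or staff is needed.
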